7.1 Demographic and Baseline Characteristics

For the subjects in MITT and safety analysis set, demographic information and Baseline values will be summarized by descriptive statistics. Categorical data will be summarized by number and percent; and quantitative data will be presented by n, mean, standard deviation, minimum value, median, and maximum value.

In general, continuous variables will be analyzed using analysis of variance (using SAS procedure 'PROC GLM') with treatment group as factor. Categorical variable will be analyzed using chi-square test or Fisher's exact test if $\geq 20\%$ of the cells have expected cell count < 5 .

The following demographic and Baseline values will be summarized.

Continuous Variables:

- Age (years)
- Body weight (kg)
- Height (cm)
- Body Mass Index (kg/m^2)
- Blood Pressure (systolic/diastolic) (mmHg)
- Pulse (bpm)

- Temperature (°C)
- CDAI
- Average Daily Stool Frequency
- Average Daily Abdominal Pain
- Total SES-CD score
- Crohn's Disease Duration (years)
- hs-CRP mg/L
- Fecal calprotectin
- IBDQ score
- WPAI and its components
- EQ-5D
- Abdominal Pain Rating Scale
- Bristol Stool Chart Score

Categorical Variables:

- Sex (male, female)
- Race
- Ethnicity
- Age (< 40, 40 to < 65, 65 to < 75, ≥ 75)
- Baseline corticosteroid use (yes, no)
- Baseline immunosuppressant use (yes, no)
- hs-CRP at Baseline (< 10 and ≥ 10 mg/L)
- Baseline fecal calprotectin (≤ 250 µg/g, > 250 µg/g)
- Crohn's disease severity (CDAI ≤ 300, > 300) at Baseline
- Baseline SES-CD (< 15, ≥ 15)
- Disease duration (≤ 3 years, > 3 years)
- Tobacco use (user, ex-user, never used, unknown)
- Alcohol use (drinker, ex-drinker, non-drinker, unknown)
- Region (US, ex-US)

7.2 Medical History

Medical and Surgical History: A complete medical and surgical history (which includes CD-onset date), history of tobacco and alcohol use, and TB history will be obtained from each subject during the Screening period. Medical history will be summarized using body system and condition/diagnosis by treatment group. No statistical tests will be performed.

Chest X-Ray Results: All subjects undergo a standard X-ray of chest (including a posteroanterior [PA] and lateral view) at Screening period. Number and percent of subjects with presence or absence of finding for the previous TB infection, calcified granulomas, Pleural scarring/thickening, and other findings will be presented by treatment group. No statistical tests will be performed.

TB Test Results: Results of PPD skin test, QuantiFERON-TB Gold test at screening visit will be summarized. Induration will be summarized descriptively using n, mean, standard deviation, minimum values, median, and maximum values. The frequency distribution of induration ≥ 5 and < 5 will be provided. QuantiFERON-TB tests will be described as positive or negative. Indeterminate QuantiFERON-TB test results will be repeated. If the second QuantiFERON-TB test is positive or indeterminate, the final assessment will be considered positive. If the second QuantiFERON-TB test is negative, the final assessment will be considered negative. No statistical tests will be performed.

TB Prophylaxis: History of use of TB Prophylaxis or initiation of TB prophylaxis will be summarized.

ECG Results: ECG results at screening will be presented as frequency distribution showing results as Normal, Abnormal (Not clinically significant), Abnormal (Clinically significant) and Unable to evaluate/missing. No statistical tests will be performed.

7.3**Previous Treatment and Concomitant Medications**

Based on generic medication names, these categories of medications used by subjects before and during the study will be summarized by number and percent for ITT and safety analysis sets for the treatment groups. No statistical tests will be performed.

The number and percent of subjects using Crohn's disease specific medications (including corticosteroids, aminosalicylates, immunosuppressants [defined as azathioprine, 6-mercaptopurine, or methotrexate], antibiotics) within past 90 days prior to the Baseline, and at the Baseline will be tabulated. In addition, the number and percent of subjects using Crohn's disease specific immunosuppressants, and biologic therapies at any time prior to Baseline will be tabulated.

8.0**Patient Disposition**

Subject disposition will be presented for subjects in the MITT and safety analysis sets using the following information by treatment group:

- Number and percent of subjects in various analysis sets by treatment group and by investigator and/or site number
- Number and percent of subjects completing double-blind induction period and discontinuing on or before Week 16 visit of induction period
- Subject disposition including the number and percent of subjects who prematurely discontinued the double-blind induction period (on or before Week 16 of induction period) by primary reason and by any reason

Summary of protocol deviations will be provided.

9.0**Study Drug Exposure and Compliance**

Study drug exposure and compliance will be summarized using the mean, standard deviation, minimum, median, and maximum. Exposure to study drug will be summarized by treatment group.

Compliance is defined as the number of capsules taken (i.e., the difference between the number of capsules dispensed and the number of capsules returned) divided by the number of capsules a subject is supposed to take each day times the length of time that the subject was in the Treatment Phase of the study (i.e., Final/Discontinuation Visit date during Treatment Phase – Day 1 [Baseline] Visit date +1). Subjects with missing data for the number of capsules returned will be excluded from the summary.

10.0 Efficacy Analysis

10.1 General Considerations

All statistical tests will be two-sided with the significance level of 0.100. Descriptive statistics will be provided. These include the number of observations, mean, standard deviation, minimum, median, and maximum for continuous variables; and number and percent for discrete variables. The analysis will be performed using SAS® (SAS Institute Inc., Cary, NC, USA).

Dose Response Modeling

Other than estimating the relative treatment effect of the investigational compound ABT-494 to placebo, one important goal of this Phase 2 study is to establish dose-response relationship to facilitate the dose selection for future Phase 3 trials. Multiple Comparison Procedure and dose-response Modeling (MCPMod) with a pre-defined group of candidates dose response curves will be tested against flat dose-response curve to best characterize the dose-response relationship.

Steps of MCPMod:

1. Choose a candidate set of S models.
2. Compute the optimum contrast for each model.
3. Use contrast test to find the significant T models while preserving FWER (one-sided significant level of 0.05).

4. Use AIC criteria to find the most significant model from the significant T models found from Step 3.
5. Use the model found from Step 4 to fit observed data from the study and make inference (e.g., to find Minimum Effective Dose (MED) or the dose achieving certain amount of maximum effect), or use all significant models to make inference about the weighted target dose of interest.

ADDPLAN or R will be used to evaluate different dose-response models and to make dose recommendation.

10.2 Primary Efficacy Analyses

This section provides the details of the primary efficacy analysis for the study.

Co-Primary Efficacy Variables:

- Proportion of subjects who achieve endoscopic remission at Week 12/16.
- Proportion of subjects who achieve clinical remission at Week 16.

Analysis Data Set for the Primary Efficacy Analysis:

The primary efficacy analysis will use the MITT analysis data set.

Imputation Method Used for the Primary Efficacy Analysis:

Missing average daily stool frequency or average daily abdominal pain at Week 16 or SES-CD at Week 12/16 will be imputed using the non-responder imputation (NRI) approach.

Statistical Method of the Primary Efficacy Analysis:

The dose-response relationships among the five ABT-494 treatment groups and placebo group will be characterized for the primary endpoints endoscopic remission at Week 12/16 and clinical remission at Week 16 using MCPMod approach. The following

models will be considered: linear, E_{max} , exponential, logistic, sigEmax, and quadratic. The MCPMod approach for trial analysis stage consists of two main steps: MCP and Mod step. The MCP step focuses on establishing evidence for a drug effect across the doses, i.e., detecting a statistically significant dose response signal for the clinical endpoint and patient population investigated in the study. This step will typically be performed using an efficient test for trend, adjusting for the fact that multiple candidate dose response models are being considered. If a statistically significant dose response signal has been established, one proceeds with determining a reference set of significant dose response models by discarding the non-significant models from the initial candidate set.

The response function will be the log odds (logit) of the proportion of subjects with endoscopic/clinical remission. The fitted curve will be shown graphically with confidence intervals for each dose. Estimates of the treatment differences in the response function and associated 95% confidences for each active dose against placebo will be calculated from the model. These results will be back-transformed to give point estimates of the difference in proportions and associated 95% confidence intervals.

Sensitivity Analysis of the Primary Efficacy Variables

The following sensitivity analyses for the primary endpoint of endoscopic remission will be conducted:

- A sensitivity analysis using observed cases, which excludes those subjects with missing post-baseline endoscopy, will also be done.

The following sensitivity analyses for the primary endpoint of clinical remission will be conducted:

- An analysis of observed cases, which excludes those subjects with missing SF or AP data at scheduled assessment visits.
- The primary analysis will be repeated using mixed-imputation. Subjects who discontinue prior to Week 16 due to lack of efficacy or adverse events will be

considered as "not achieved" for the clinical remission. Subjects who discontinue for other reasons will be categorized according to LOCF.

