This period will begin at the Baseline Visit (Week 0) and will end at the Week 16 Visit. At the Baseline Visit, subjects who meet all the inclusion criteria and none of the exclusion criteria described in the protocol (Section 5.2.1 and Section 5.2.2) will be

enrolled into the study and randomized to double-blind induction period. The randomization at Baseline will be stratified by endoscopic disease severity (SES-CD < 15 and \geq 15), prior anti-TNF use (naïve and experienced), and by participation in the substudy of the gene expression in intestinal biopsies (Yes and No). As part of the randomization at Baseline, subject will be randomly assigned (1:1) to have their follow-up ileocolonoscopy done at Week 12 or Week 16. During this period of the study, subjects will visit the study site at Weeks 2, 4, 8, 12 and 16. A \pm 3-day window is permitted around scheduled study visits. The last dose of study drug during this period is taken the evening prior to the Week 16 visit.

However, the stratification factor Prior anti-TNF use (naïve and experienced) was added under Amendment 3, and there are less than 10 anti-TNF naïve subjects enrolled under Amendment 3. Therefore, the Prior anti-TNF use will not be included in all analysis as a stratification factor.

Subjects may discontinue study drug treatment at any time during study participation. Subjects that end study participation early will have an Early Termination (ET) Visit and complete the procedures outlined for the ET Visit in [Table 1](#) as soon as possible after the last dose of study drug and preferably prior to the administration of any new therapies.

36-Week Extension Phase

At Week 16, subjects who have completed the induction period will be re-randomized in a ratio of 1:1:1 to one of the three double-blinded doses of ABT-494 3 mg BID, 6 mg BID or 12 mg BID. The re-randomization will be stratified by dose received during the first 16 weeks, and overall response (responder versus non-responder) at Week 16. The subjects who were re-randomized at Week 16 to ABT-494 24 mg QD prior to Protocol Amendment 2 will continue to receive the same double-blind dose until Week 52/PD.

The central reader endoscopic score will be used for calculating the Endoscopic response for the evaluation of the efficacy endpoints. However, for stratification at the time of re-randomization, the endoscopic score at BL from central reader and the endoscopic

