4.3 Sample Size

Approximately 210 subjects will be equally allocated to five treatment groups and the placebo group, representing a randomization ratio of 1:1:1:1:1. The sample size for this study is based on the expected proportion of subjects who achieve endoscopic remission at Week 12/16 and on the expected proportion of subjects who achieve clinical remission at Week 16. Assuming an endoscopic remission (as well as clinical remission) rate of 12% in the placebo arm and maximum of 35% in at least one of the ABT-494 BID treatment arms (3 mg BID, 6 mg BID, 12 mg BID and 24 mg BID) at Week 12/16, a sample size of 35 subjects per treatment group is sufficient to test for the presence of a dose response signal, to select the best dose response model for the observed data out of a prespecified set of candidate models, and to estimate target doses of interest (e.g., the minimum effective dose, MED) via modeling using MCP-Mod (Multiple comparison procedure and modeling) approach. This approach provides at least 80% average power to detect a dose effect at 5% level of significance (one-sided) with the linear, E_{max} , exponential, logistic, and sigEmax models pre-specified as likely candidates to characterize the dose-response for ABT-494 for the two co-primary endpoints of clinical and endoscopic remission.

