5.2 Variables Used for Stratification of Randomization

At Baseline, subjects will be randomized in a 1:1:1:1:1:1 ratio to receive one of the six treatment groups (double-blind ABT-494 induction doses or matching placebo).

The following are the treatment groups:

Group 1: ABT-494 3 mg BID

Group 2: ABT-494 6 mg BID

Group 3: ABT-494 12 mg BID

Group 4: ABT-494 24 mg BID

Group 5: ABT-494 24 mg QD

Group 6: Placebo

The randomization at Baseline will be stratified by endoscopic disease severity (SES-CD < 15 and \geq 15), prior anti-TNF use (naïve and experienced), and by participation in the substudy of the gene expression in intestinal biopsies (Yes and No). As part of the randomization at Baseline, subjects will be randomly assigned (1:1) to have their follow-up ileocolonoscopy done at Week 12 or Week 16.

At Week 16, subjects who have completed the induction period will be re-randomized in a ratio of 1:1:1 to one of the three double-blinded doses of ABT-494 3 mg BID, 6 mg BID or 12 mg BID. The re-randomization will be stratified by dose received during the first 16 weeks, and overall response (responder versus non-responder) at Week 16. The

subjects who were re-randomized at Week 16 to ABT-494 24 mg QD prior to Protocol Amendment 2 will continue to receive the same double-blind dose until Week 52/PD.

Overall response consists of both Endoscopic response and Clinical response. The central reader endoscopic score will be used for calculating the Endoscopic response for the evaluation of the efficacy endpoints. However, for stratification re-randomization, the endoscopic score at baseline from central reader and the endoscopic score at Week 12 or Week 16 from site local reader will be used in order to determine response status.

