The MMRM model will be used for continuous efficacy variables with longitudinal data as the primary analysis. The MMRM model includes the baseline values as covariate; randomization strata, treatment, time point and treatment-by-time point interaction as fixed effects; and subjects within treatment as random effect. An unstructured (co)variance structure will be used to model the within-subject error. The comparison at a time point will be the contrast between treatments at that time point. Satterthwaite's approximation will be used to estimate denominator degrees of freedom.

Imputation of Missing Dates

For Baseline, efficacy, and safety parameters, if the day and/or month are missing, the following conventions will be used to impute the missing dates:

- 01 for missing start day
- End of month for missing end day
- January 1st for missing start month
- December 31st for missing end month

In case of partially missing AE start and stop dates, the dates will be imputed by comparing to first dose date of study medication so that the corresponding AEs will be

made treatment-emergent whenever possible. If the start date of an AE is partially missing and the month is the same as the start date of a new therapy, the AE will be made treatment emergent to the new therapy.

In case of missing or partially missing study drug dosing dates, the dates will not be imputed. Subjects will be treated as not receiving dose on that date.

Rule for CDAI Calculation

Up to 14 days of diary entries will be evaluated from the ePRO tool for the CDAI calculation for each visit. The diary entries on the days the subjects receive endoscopy preparation medications, the day of endoscopy procedure, and 2 days after endoscopy procedure will be excluded. For each CDAI subscore, the available scores from the most recent diary days (at least 4 days, up to 7 days) prior to actual day of the study visit will be summed, and then multiplied by the corresponding multiplier to get subtotal score. If available diary entries are fewer than 7 days, the subtotal score will be calculated as (summed total available score/number of days) \times 7 \times corresponding multiplier. The three subtotal scores that are based on ePRO (number of liquid/very soft stools, abdominal pain rating, and general well-being) will then be rounded to one decimal. The final CDAI is rounded to a whole number.

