- The proportion of subjects who achieve $> 50\%$ reduction from Baseline in SES-CD or endoscopic remission at Week 12/16.
- The proportion of subjects who achieve modified clinical remission at Week 16 among subjects with an average daily SF ≥ 4.0 or average daily AP ≥ 2.0 at Baseline.

For categorical efficacy endpoints for Induction Period, the pairwise comparisons for the difference in proportions of subjects between treatment groups and placebo group will be analyzed using the CMH test adjusted for Crohn's disease severity (SES-CD < 15 , ≥ 15) at Baseline. Additionally, the CMH-based 95% confidence interval for the difference in proportions will be provided. The 95% confidence interval for the difference in proportions within each Crohn's disease severity (SES-CD < 15 , ≥ 15) at Baseline category will be calculated based on normal approximation.

The non-responder imputation will be used for subjects with missing data at the endpoint evaluated. The last observation carried forward (LOCF) method will also be used as the sensitivity analyses for the secondary endpoints.

In general, continuous secondary efficacy variables with repeated measurements will be analyzed using a Mixed Effect Repeated Measure (MMRM) model. The mixed model includes the categorical fixed effects of treatment, Crohn's disease severity (SES-CD < 15, ≥ 15) at Baseline, week and treatment-by-week interaction and the continuous fixed covariates of baseline measurement. An unstructured variance-covariance matrix will be used. If convergence is not achieved, other variance-covariance matrix will be explored until coverage. The parameter estimations will be based on assumption of data being missing at random and using the method of restrictive maximum likelihood (REML).

Continuous secondary efficacy variables will also be analyzed using an Analysis of Covariance (ANCOVA) model including factors for treatment group and Crohn's disease severity (SES-CD < 15, ≥ 15) at Baseline, and Baseline values as a covariate. The MMRM analysis is considered primary for inferential purposes.

The additional endpoints include:

- Proportion of subjects who achieve clinical remission over time in Induction Period.
- Proportion of subjects who achieve clinical response over time in Induction Period.
- Proportion of subjects who achieve CDAI < 150 over time in Induction Period.
- Proportion of subjects with decrease in CDAI ≥ 70 points from Induction Baseline over time in Induction Period.

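### The induction SAP names no SES-CD term in the co-primary MCP-Mod, although SES-CD stratified the randomization and the secondary analyses adjust for it; adding it would be a small, cheap gain in precision

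*SAP*

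**What the plan says.** **Primary analysis.** Induction SAP 10.2 analyses both co-primary endpoints by MCP-Mod on the MITT set: "The response function will be the log odds (logit) of the proportion of subjects with endoscopic/clinical remission". It names no covariate or stratum. Neither do the MCP-Mod steps in SAP 10.1, the multiplicity text in SAP 10.4, or protocol 8.1.6.1.1.

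**Randomization.** SAP 5.2: "The randomization at Baseline will be stratified by endoscopic disease severity", cut at 15, with prior anti-TNF use and gene-expression substudy participation as the other factors.

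**Other induction analyses.** In SAP 10.3 categorical endpoints "will be analyzed using the CMH test adjusted for" SES-CD at that cut, and the MMRM and ANCOVA carry the same factor. SAP 6.0 says of the general repeated-measures model: "The MMRM model includes the baseline values as covariate; randomization strata, treatment, time point and treatment-by-time point interaction as fixed effects".

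**Dropped strata.** SAP 4.2 removes one factor, because fewer than 10 anti-TNF-naïve subjects were enrolled under Amendment 3: "Therefore, the Prior anti-TNF use will not be included in all analysis as a stratification factor". SES-CD is not removed anywhere.

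**Power.** SAP 4.3: "This approach provides at least 80% average power", at one-sided 5%, with 35 per arm, 12% remission on placebo and at most 35% on a BID arm.

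The point concerns the induction SAP only. The extension SAP does not adjust its efficacy comparisons for SES-CD.

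**The concern.** A factor used to stratify randomization is normally carried into the analysis. If it predicts outcome, balancing on it reduces the true variability of the arm comparisons, and an analysis that ignores it reports a standard error that is slightly too large. The test stays valid but becomes conservative.

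A prognostic effect on endoscopic remission is plausible from the definition alone. Remission needs SES-CD of 4 or less and a fall of at least 2 points. A subject starting at 15 or above must fall by at least 15 − 4 = 11 points; an eligible subject starting between 4 and 14 needs a fall of 2 to 10. Clinical remission rests on stool frequency and abdominal pain, so its link to SES-CD may be weak.

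The plan is also uneven. Clinical remission at Week 12 and composite remission at Week 16 are listed as secondary endpoints and are adjusted for SES-CD. Clinical remission at Week 16 and endoscopic remission, which make up that composite, are not adjusted in MCP-Mod. At stake is some precision in the dose-response analysis, which SAP 10.1 calls an important goal for choosing Phase 3 doses.

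**Working it through.** **Inputs from the documents:** 35 per arm; 12% and 35%; one-sided 5% controlled over the candidate models; the five shapes in SAP 4.3 (linear, Emax, exponential, logistic, sigEmax).

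**Assumed, because the documents do not give them:** the candidate parameters, the share of subjects with SES-CD ≥15, and the between-stratum odds ratio (OR) for remission. BID doses enter as 0, 6, 12, 24 and 48 mg/day.

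**1. The stated power.** Arm logits have variance 1/(n·p·(1−p)), with shape-based contrasts and a multivariate-normal critical value. One parameter set gives average power of 83.3% (single models 75% to 87%). Over 108 parameter sets the average runs from 80.1% to 84.8%, median 82.7%. The stated floor is therefore met without adjustment. Adding the quadratic model listed in SAP 10.2 gives 83.0%; placing the 24 mg QD arm at 24 mg/day gives 83.8%.

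**2. Adding the stratum, by simulation.** The maximum-contrast test used critical value 1.972 and assumed shapes in mg/day: Emax ED50 9.6; exponential delta 14; logistic ED50 18, delta 4.5; sigEmax ED50 14, h 3; and linear. Unadjusted: a Firth-penalised logit per arm. Adjusted: Firth logistic regression on arm plus stratum, standardised to the stratum mix, with delta-method covariance. Each power figure rests on 50,000 runs (Monte Carlo SE about 0.17 points).

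| Share ≥15 | OR | Unadjusted | Adjusted | Gain (points) |
|---|---|---|---|---|
| 50% | 1 | 81.9% | 81.9% | 0 |
| 50% | 2 | 82.1% | 82.6% | 0.5 |
| 50% | 3 | 81.8% | 83.2% | 1.4 |
| 50% | 6 | 82.9% | 85.9% | 3.0 |
| 30% | 1 | 81.6% | 81.6% | 0 |
| 30% | 2 | 81.9% | 82.3% | 0.4 |
| 30% | 3 | 81.9% | 82.9% | 1.0 |
| 30% | 6 | 82.5% | 84.4% | 1.9 |

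At 50:50 the adjusted-to-unadjusted variance ratio for top dose minus placebo is 1.00, 0.975, 0.94 and 0.87 at OR 1, 2, 3 and 6.

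**3. Adding the stratum, by Fisher information.** With marginal rates held at the stated values and a 50:50 split, the gains are 0.5, 1.3 and 2.5 points at OR 0.5, 0.33 and 0.2 (≥15 against <15). Over shares of 30% to 70% the range is 0.4 to 2.8 points. The confidence interval for a standardised risk difference narrows by 0.8% to 5.6%.

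**4. In subjects.** Unadjusted power at OR 3 is 82.1% with 35 per arm and 83.2% with 36. At OR 6 it is 82.7% with 35 and 86.2% with 38. So adjustment is worth about 1 and about 3 subjects per arm.

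**5. Scale.** For 35% against 12%, the log odds ratio is 1.373 with SE √[1/(35·0.12·0.88) + 1/(35·0.35·0.65)] = 0.629, so z = 2.18. With a stratum term at OR 0.33, the conditional estimate is 1.440 with SE 0.644, so z = 2.24. The logit SE rises, but the estimate rises more. A narrower interval appears only after standardising back to the marginal difference.

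**6. Type I error (illustrative).** In the simulation the unadjusted test rejects in 3.9% of null runs at OR 1 because events are sparse, 3.4% at OR 3 and 3.2% at OR 6. The adjusted test gives 3.8% at OR 3 and 4.1% at OR 6. With 350 per arm at OR 6 the figures are 4.3% and 5.0%, which isolates the part due to the omitted stratum. A single linear contrast gives 4.2% to 4.8% unadjusted and 4.5% to 4.9% adjusted. Nothing exceeds the nominal 5%.

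**The case against.** The strongest reply is that this is a preference. No stated figure is wrong, the test is not inflated, and the protocol also leaves MCP-Mod unadjusted while adjusting the secondary analyses, so the split may be deliberate. SES-CD was never promised in MCP-Mod, whereas anti-TNF use was promised in the secondary models and its removal had to be explained. All of that stands, and it limits the weight of the point.

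Second, the CMH sentence in SAP 10.3 speaks of categorical efficacy endpoints generally, without the word secondary that protocol 8.1.6.2.1 uses. It could be read to include the co-primaries, and SAP 10.5 analyses them by SES-CD subgroup. The wording is ambiguous, but on either reading the MCP-Mod test and the dose selection remain unadjusted.

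Third, the size depends on assumed inputs and on four BID arms with five models, while SAP 10.2 has five active groups and six models. The figures therefore describe the sample-size scenario. The type I error figures also depend on a Firth penalty that the SAP does not specify. Both limits are real, though neither changes the conclusion that the gain is small.

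Fourth, a covariate on the logit scale would shift the target from a marginal to a conditional effect. That is correct for a bare covariate; standardisation avoids it at the price of one more step.

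**Conclusion.** The concern holds, as an optional improvement. The co-primary MCP-Mod omits a factor that the trial randomised by and adjusts for elsewhere, without saying why. Under the assumed splits and between-stratum odds ratios of 2 to 3, the cost is about 0.4 to 1.4 points of average power. At an odds ratio of 6 it is about 2 to 3 points, and at 1 it is zero. The claim of at least 80% power stands without the change, and error control is not threatened. The benefit is more likely for endoscopic remission than for clinical remission. These sizes rest on an assumed prognostic strength, stratum split and candidate-model parameters.

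**What to change.** In induction SAP 10.2:

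- Make the first stage a logistic regression of remission on treatment arm and SES-CD stratum (<15, ≥15).
- Standardise the arm estimates to the MITT stratum mix, so that the target remains the marginal difference in proportions. Pass the estimates and covariance matrix to the contrast tests and model fits, and say how the AIC step in SAP 10.1 is computed from them.
- State a rule for sparse cells, for example Firth penalisation. About 0.12 × 35 = 4.2 placebo remitters are expected, and the chance of none is 0.88^35 = 1.1%, with or without the stratum.
- Keep the unadjusted analysis as a sensitivity analysis.

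If SES-CD is left out on purpose, one sentence giving the reason is enough.

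The cost is about one SAP paragraph plus programming of the standardisation; the stratum is already collected. If Firth is chosen, it shrinks estimates slightly: a 12% placebo rate becomes (4.2 + 0.5)/36 = 13.1%, as it would in an unadjusted Firth fit. The extension SAP (3.0) says the induction SAP was signed off before the December 2016 database lock, so an adjusted analysis added after that lock should be labelled supportive.
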